1.0 Objectives

1.1 This study seeks to quantify the near visual performance and subjective visual acceptance of toric contact lenses as compared to spherical lenses in an astigmatic cohort of patients. We also aim to explore associations between tear LTB4 concentration, eye comfort, visual performance, and subjective visual quality after 6-8 hours (full day of wear) toric and spherical contact lens wear.

1.2 Primary Hypotheses: Subjects will have better near visual acuity and near visual performance with toric, as opposed to spherical, contact lens correction. As such, the following hypotheses will be tested:

H01: There is no statistically significant difference in near visual acuity or near vision performance between contact lenses corrections

Ha1: There is a statistically significant difference in visual acuity or vision performance between contact lenses corrections

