5.0 Number of Subjects

5.1 The proposed single-site study will be conducted at the University of Houston College of Optometry. Up to 30 subjects will be screened for study inclusion, with the goal of completing 24 subjects.

Source data will be collected on paper case report forms and then double entered electronically into a database by trained personnel prior to locking the dataset for analysis.

5.2 In this within-subject crossover design, a paired T-test will be used to compare visual acuity performance, contact lens discomfort, subjective visual quality and LTB4 concentration following toric lens wear to spherical contact lens wear. We will use a two-sided independent T-test to ensure there are no carry over or period effects in our cross-over design, although it is not anticipated. As a secondary outcome, subjects will be asked their preference of contact lenses in a two-alternative forced choice format.

FULL PROTOCOL TITLE: Toric Contact Lens Digital Performance and Comfort Study

One-sample binomial tests will be used to test the hypothesis that the probability of preference to toric lens and spherical lenses are equally likely. Linear mixed model or generalized linear model, as appropriate, will be carried out to examine the associations between eye comfort, visual performance, subjective visual quality and LTB4 concentration during toric and spherical contact lens wear.

We aim to test the hypothesis that $H_0: \Delta=0$ v. $H_1: \Delta \neq 0$ using a two-sided test with significance level $\alpha=0.05$, where Δ is the underlying benefit for treatment contact lenses versus spherical contact lenses in this cross-over design. Our previous work found that toric correction improved visual acuity compared to spherical correction by 6 and 11 letters for high and low contrast logMAR, respectively ($P < 0.001$).¹⁰ To demonstrate an improvement of this amount or more it will require at least 24 and 15 subjects with a $P=0.05$ and 80% power. The dynamic visual acuity test is novel and has not been used previously to allow sample size estimates. A total of 30 subjects will be enrolled to allow for up to 20% dropout/screen-failure/missing data and have 24 subjects complete. We will randomize an equal number of subjects to each group (i.e., group A receives treatment 1 in period 1 and treatment 2 in period 2; group B receives treatment 2 in period 1 and treatment 1 in period 2).

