9.0 Study Endpoints

9.1 The primary study endpoints will compare toric to spherical lenses for:

- Near visual acuity

The secondary study endpoints will compare toric to spherical lenses for:

- Other near visual performance outcomes
 - Reading speed, reading sentences acuity, digital device interaction, dynamic visual acuity
- Subjective eye comfort and visual acceptance during contact lens wear
 - Association between subjective comfort surveys and tear TLB4 concentration

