9.2 This is a minimal risk study so safety endpoints are not required

10.0 Procedures Involved

10.1 The study is a clinical trial and will be registered on ClinicalTrials.gov prior to subject enrollment.

10.2 Patients will be seen for 5 visits over a period of approximately 1 month. Visit 1 will determine subject eligibility for the study. Visits 2 and 4 are contact lens follow-up visits. Visits 3 and 5 are study outcome visits. Tests of visual performance at a near reading distance will be evaluated with an iPad application developed by [name]. These applications are designed for research purposes only and are not commercially available. The applications can measure reading speed and provide information on how a subject interacts with the electronic device (e.g. blink rate, working distance from the device, scrolling and zooming on the page, etc.).

10.3 Subjects will be randomized to start with either toric lenses or spherical correction (FDA approved lenses will be utilized).

Overview of Visit Procedures (Assessments)

FULL PROTOCOL TITLE: Toric Contact Lens Digital Performance and Comfort Study

A masked examiner will perform all outcome measures.

| | Visit 1 Baseline and Fit Lens 1 | Visit 2 day 3±1 | Visit 3 – day 10±2 | | Visit 4 day 13±1 | Visit 5 day 20±2 |
|--|--|-------------------------|-----------------------|---------------|-------------------------|---------------------|
| | | Follow- up Lens 1 | Outcomes Lens 1 | Fit Lens 2 | Follow- up Lens 2 | Outcomes Lens 2 |
| Informed consent | X | | | | | |
| Ocular/medical/contact lens history | X | | | | | |
| Ocular symptoms (CLDEQ-8) ⁸ | X | | X | | | X |
| Auto-refraction and keratometry | X | | | | | |
| Slit lamp exam with NaFl staining | X | | | | | |
| Manifest refraction | X | | | | | |
| Accommodation and phoria | X | | | | | |
| Near logMAR HCHL & LCHL acuity OU | X | | X | | | X |
| NAVQ survey ⁵ | X | | X | | | X |
| Radner reading sentences, dynamic acuity measurement and functional vision test with iPad ⁴ | X | | X | | | X |
| Tear collection | X | | X | | | X |
| Study lens order randomization | X | | | | | |
| Insertion of CL and settling (15 min) | X | | | X | | |
| Clinical CL vision and fit assessment, over-refraction, and power adjustment if indicated | X | X | | X | X | |
| Removal of study lens and slit lamp exam with NaFl staining | | X | X | | X | X |

FULL PROTOCOL TITLE: Toric Contact Lens Digital Performance and Comfort Study

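### The primary hypothesis and the primary endpoint differ in scope, no success rule covers the two acuity contrasts, and the carry-over pretest inflates the error rate even for one contrast

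*Protocol*

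**What the plan says.** **Hypothesis.** Under Primary Hypotheses, protocol 1.2 gives "H01: There is no statistically significant difference in near visual acuity or near vision performance between contact lenses corrections". The alternative has the same scope: "There is a statistically significant difference in visual acuity or vision performance between contact lenses corrections". The sentence introducing them joins acuity and performance with *and*; H01 and Ha1 join them with *or*.

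**Endpoints.** Section 9.1 opens with "The primary study endpoints will compare toric to spherical lenses for" and lists near visual acuity alone. The secondary list includes "Reading speed, reading sentences acuity, digital device interaction, dynamic visual acuity".

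**What acuity means.** The visit table in section 10 has "Near logMAR HCHL & LCHL acuity OU", that is, two binocular acuity measures at each outcome visit.

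**Sample size.** Section 5.2 takes earlier effects of 6 letters (high contrast) and 11 letters (low contrast) and concludes that "it will require at least 24 and 15 subjects" for 80% power. The same paragraph describes one hypothesis about one delta, "using a two-sided test with significance level" 0.05, without saying which contrast delta refers to.

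**SAP.** The Statistical Plan names no primary outcome and applies a 0.05 threshold to the lens comparisons, with no order or adjustment. It first tests for carry-over at 0.10 and, if carry-over is found, confines hypothesis tests to period one.

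**The concern.** A reader cannot tell from these documents what would count as a positive primary result. Sections 1.2 and 9.1 give the performance outcomes two different ranks. Even if 9.1 governs, the single primary endpoint is two measurements, each with its own sample size, and the rule for combining them is absent. The nominal 5% then depends on a choice that could be made once results are known.

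The SAP adds a second, separate problem. Choosing between a two-period and a period-one analysis by means of a preliminary test on the same data changes the error rate of the final test. This would affect a trial with one perfectly defined primary outcome, and it limits what any rule for the two contrasts can achieve.

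**Working it through.** **1. The plan's own figures.** Enrolment reproduces: 24 / (1 − 0.20) = 30. The sample sizes of 24 and 15 can be neither reproduced nor refuted, because no SD of the paired differences is given. Solving the noncentral-t power of a paired t-test for 80% at two-sided 0.05 gives the SDs they imply:
- High contrast, n = 24, 6 letters: SD about 10.0 (6/10.05 = 0.597).
- Low contrast, n = 15, 11 letters: SD about 14.1 (11/14.14 = 0.778).

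These back-solved SDs are an assumption. They are used only for power.

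**2. Either contrast suffices, each at 0.05.** Independent tests: 1 − 0.95² = 9.75%. Perfectly correlated tests: 5%. Simulated paired t-tests with n = 24 give the values between:

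| Assumed correlation | Either suffices |
|---|---|
| 0.5 | 9.1% |
| 0.7 | 8.4% |
| 0.9 | 7.1% |

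**3. Both contrasts required.** The rate is at most 5%, since a false claim needs at least one true null to be rejected at 0.05.

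**4. Literal scope of 1.2.** Two contrasts plus one test for each of the four performance items in 9.1 make six tests. If independent: 1 − 0.95⁶ = 26%. This is a ceiling, as the outcomes are probably correlated; at common correlations of 0.5 to 0.9 the simulated rate is 21% to 11%.

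**5. Carry-over pretest.** Setting: 12 subjects per sequence; no lens, period or carry-over effect; t-test on subject means at 0.10; if significant, a two-sample t-test on period one, otherwise the paired test. One contrast only:

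| Assumed within-subject correlation | With pretest and fallback | Full two-period analysis |
|---|---|---|
| 0.3 | 7.6% | 5% |
| 0.5 | 8.1% | 5% |
| 0.7 | 8.7% | 5% |
| 0.9 | 9.4% | 5% |

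Repeat runs gave 7.5% to 9.4%. Holm applied to p-values from the fallback procedure still gave about 6% to 9%, against 3.6% to 4.7% on two-period p-values.

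**6. Power of the candidate rules.** 24 completers, a 6-letter high-contrast effect and the SDs from step 1. Unadjusted power is 80% for high contrast and 95% for low contrast at 11 letters. A smaller low-contrast effect is worth checking because protocol 2.2 reports earlier near acuity gains of half to one line, which is 2.5 to 5 letters if a line is five letters (assumption).

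| Low-contrast effect | High-contrast power under Holm | Power if both must succeed |
|---|---|---|
| 11 letters | about 79–80% | about 76–80% |
| 5 letters | about 70–71% | about 35–38% |
| 2.5 letters | about 70% | about 13% |

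The ranges cover contrast correlations of 0.5 to 0.9; the 76% end of the first row is at correlation 0. Low-contrast power under Holm is 91% to 94% at 11 letters. The floor for high contrast is its power at 0.025, which is 70%.

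**The case against.** The strongest reply is that the plan can be read coherently. Section 9.1 may narrow 1.2, because it treats acuity as one kind of near performance and ranks the rest below it. Recruiting to 24 completers, the larger of the two sample sizes, fits a rule that both contrasts must succeed, and under that rule having two contrasts inflates nothing. This stands as a possible intention, but no section states it.

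Some stronger readings are tempting and are not supported:
- **That Ha1 makes either contrast sufficient.** Its *or* joins acuity and performance. It does not address high versus low contrast, and the introductory sentence of 1.2 uses *and*.
- **That the error rate is 7% to 9%.** This needs both an either-suffices rule and a correlation of about 0.5 to 0.9. The documents give neither.
- **That the number of tests is larger still.** Section 10.2 mentions "blink rate, working distance from the device, scrolling and zooming on the page", but as open-ended examples. No section says each is tested separately.
- **That the SAP was written with outcome data in hand.** It is dated 20 December 2021 and is in the past tense, and protocol 8.1 expected analyses to finish in Fall/Winter 2021. This raises the question without answering it.

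It is also fair to say that the pretest simulation uses t-tests throughout, whereas the SAP allows Mann-Whitney and does not name the period-one test. The exact percentages depend on those choices.

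**Conclusion.** The point holds. The mismatch between 1.2 and 9.1 and the missing rule for the two contrasts are certain from the text. The size of the inflation is conditional: none if both contrasts are required, 5% to 9.75% if either suffices, and up to 26% as a ceiling if the performance outcomes also count.

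The pretest is a separate defect. It takes one contrast to about 7.5% to 9.4%, assuming within-subject correlation of 0.3 to 0.9, no true carry-over and t-tests. Settling the rule for the contrasts would therefore not by itself secure 5% while the fallback remains.

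**What to change.** 1. Reword H01 and Ha1 in 1.2 to near visual acuity only, matching 9.1, with all other outcomes secondary.
2. State one rule for the two contrasts in 5.2 and in the SAP: one named primary contrast; or both significant at 0.05; or Holm at two-sided 0.05 (smaller p-value against 0.025 and, if significant, the larger against 0.05).
3. Take the primary p-values from the full two-period analysis whatever the carry-over test shows, and report that test descriptively.
4. If the rule is set after outcome data were seen, say so and show unadjusted and adjusted p-values for both contrasts. This gives transparency but does not restore pre-specification.

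**Cost.** Wording only, with no new subjects. The power cost decides between the rules. Naming one contrast leaves that contrast's power unchanged. Holm costs high contrast about 1 point if the low-contrast effect is 11 letters, but about 9 to 10 points if it is 5 letters or fewer. A both-must-succeed rule is affordable at the planned effects and loses more than half its power at a 5-letter low-contrast effect. The sponsor should choose with that sensitivity in view.

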2.0 Background

2.1 Americans spend over 10 hours a day consuming media on smartphones, digital tablets and home computers.¹ The visual demands of this type of work require the use of sustained clear near and intermediate vision. Previous work in our labs has shown small but measurable improvements in visual acuity for toric lenses² as compared to spherical correction. Unfortunately, standard in office high contrast, high luminance testing is often not helpful in demonstrating potential improvement in real-world tasks afforded by toric lenses.

2.2 Dynamic visual acuity has been used in sports vision assessment and training in the past, but little is published on the topic. It is more robust than traditional visual acuity measures in being a detection rather than recognition task, is always of equal difficulty, there is limited time for observer adjustments such as blinking/squinting, and a staircase procedure ensures a definitive endpoint. Wolffsohn's lab has recently developed an iPad-based application to assess dynamic visual acuity (**see Appendix A**).

Woods et al³ began exploring patients' preferences conducting real-world tasks such as the ability to locate a web page, read a newspaper or use a computer. They showed that while the difference in standard acuity testing was small, patients reported significant subjective improvements in driving, watching a television, and using a desktop computer, among others.³ Wolffsohn and colleagues recently developed iPad based applications that can quantify reading performance on digital devices while the user performs reading tasks (see also **Appendix B**).⁴ The user's face is analyzed in real-time by the front facing camera to allow working distance and blinks to be tracked. Swipes, changes in magnification and the time to complete the task are also assessed. This group also developed a Near Activity Visual Questionnaire (NAVQ) (**Appendix C**) to quantify subjective near visual function.⁵

FULL PROTOCOL TITLE: Toric Contact Lens Digital Performance and Comfort Study

The [name] lab recently utilized these applications to assess near visual performance with spherical vs. toric soft contact lenses and found that toric correction improved near high-and low-contrast visual acuity by 0.5 to 1 full line, and enabled individuals to read one line smaller text on the iPad (STUDY00000682). The majority of subjects preferred the toric correction, though this was based on visual performance alone, and not ocular comfort.⁶

2.3 Contact lens discomfort can affect wearing time and potentially lead to dropout, particularly in the first year of wear.^{6,7} According to the Tear Film Ocular Surface (TFOS) Contact Lens Discomfort report, lens design, material and the interaction between the contact lens and ocular surface are potential factors associated with contact lens discomfort.⁷ Toric lenses have been reported to be less comfortable than spherical lenses; however previous studies mainly explored older lens materials and designs.⁷ Additionally, it is thought that contact lens discomfort may be more related to subjective visual quality (Questions 3a and 3b in Contact Lens Dry Eye Questionnaire-8) (**Appendix D**).⁸ However, the effect of modern toric and spherical daily disposable soft contact lenses on the association between contact lens discomfort, subjective visual quality and visual function has not been investigated. Symptomatic lens wearers usually report discomfort prior to reducing lens wear time.⁹ Recently, it has been shown that contact lens discomfort was related to upregulation of tear eicosanoid biomarkers. Masoudi et al found a higher tear concentration of Leukotriene B4 (LTB4) at the end of the day in symptomatic soft contact lens wearers compared to asymptomatic contact lens wearers.⁹

The purpose of this study is to quantify digital visual performance and subjective visual acceptance and its association with ocular comfort and subjective visual quality, during toric contact lens wear as compared to spherical lens wear in low to moderate astigmatic patients after a full day of contact lens wear. We also aim to explore the association between tear LTB4 concentration, eye comfort, visual performance, and subjective visual quality after 6-8 hours (full day) of toric and spherical contact lens wear.

3.0 Inclusion and Exclusion Criteria

3.1 ALL SUBJECTS must be/have:

- Able to speak and read English at a high school level / have at least a high school diploma or equivalent (by self-report) 18 to 39 years of age (inclusive)
- Plano to -6.00 D vertex corrected sphere power and -0.75 to -1.50 vertexed cylinder power in each eye
- Best corrected acuity of 20/25 or better in each eye
- Self-report of at least 4 hrs/day using digital devices
- Willing not to wear their habitual contact lenses or use artificial tears or other solutions for at least 24 hours
- No history of ocular pathology or surgery
- No active ocular infection or clinically significant ocular inflammation
- Current/established full time (>6 days per week, >8 hours per day) soft contact lens wearer

FULL PROTOCOL TITLE: Toric Contact Lens Digital Performance and Comfort Study

- Asymptomatic soft contact lens wearer (CLDEQ-8 score <12 at baseline)
- No significant binocular vision abnormality (i.e., tropia, convergence or accommodative insufficiency)
- No gas permeable lens wear for at least 3 months
- Not an optometrist
- Not pregnant/lactating (by self-report)
- Willing to wear lenses at least 8 hours each day during the study period

3.2 Potential subjects will be initially screened for study eligibility by phone/in person discussion and through collection of baseline data at visit 1.

3.3 *Vulnerable Populations*

The following vulnerable populations will be excluded from the study:

1. Adults unable to consent
2. Individuals who are not yet adults (infants, children, teenagers under age 18)
3. Prisoners
4. Pregnant/lactating women (by self-report) will not be enrolled as hormone changes can affect the ocular surface and comfort with contact lenses
5. Students for whom the principal investigator has direct access to/influence on grades will only be consented and examined by other investigators.

4.0 Vulnerable Populations

Students for whom one of the principal investigators has direct access to/influence on grades would be consented and seen by another investigator for all visits. The following vulnerable populations will be excluded from the study:

1. Pregnant women
2. Neonates of uncertain viability or non-viable neonates
3. Prisoners
4. Children
5. Cognitively impaired adults

5.0 Number of Subjects

5.1 The proposed single-site study will be conducted at the University of Houston College of Optometry. Up to 30 subjects will be screened for study inclusion, with the goal of completing 24 subjects.

Source data will be collected on paper case report forms and then double entered electronically into a database by trained personnel prior to locking the dataset for analysis.

5.2 In this within-subject crossover design, a paired T-test will be used to compare visual acuity performance, contact lens discomfort, subjective visual quality and LTB4 concentration following toric lens wear to spherical contact lens wear. We will use a two-sided independent T-test to ensure there are no carry over or period effects in our cross-over design, although it is not anticipated. As a secondary outcome, subjects will be asked their preference of contact lenses in a two-alternative forced choice format.

FULL PROTOCOL TITLE: Toric Contact Lens Digital Performance and Comfort Study

One-sample binomial tests will be used to test the hypothesis that the probability of preference to toric lens and spherical lenses are equally likely. Linear mixed model or generalized linear model, as appropriate, will be carried out to examine the associations between eye comfort, visual performance, subjective visual quality and LTB4 concentration during toric and spherical contact lens wear.

We aim to test the hypothesis that $H_0: \Delta=0$ v. $H_1: \Delta \neq 0$ using a two-sided test with significance level $\alpha=0.05$, where Δ is the underlying benefit for treatment contact lenses versus spherical contact lenses in this cross-over design. Our previous work found that toric correction improved visual acuity compared to spherical correction by 6 and 11 letters for high and low contrast logMAR, respectively ($P < 0.001$).¹⁰ To demonstrate an improvement of this amount or more it will require at least 24 and 15 subjects with a $P=0.05$ and 80% power. The dynamic visual acuity test is novel and has not been used previously to allow sample size estimates. A total of 30 subjects will be enrolled to allow for up to 20% dropout/screen-failure/missing data and have 24 subjects complete. We will randomize an equal number of subjects to each group (i.e., group A receives treatment 1 in period 1 and treatment 2 in period 2; group B receives treatment 2 in period 1 and treatment 1 in period 2).

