Title

Toric Contact Lens Digital Performance and
Comfort Study

NCT number

NCT04772560

Document date

20 Dec 2021

Statistical Plan

The outcome measures for the two contact lens designs were first analyzed using the Grizzle model. The data were tested for the presence of a carry-over effect by examining the average of outcomes in the two periods within subjects between the two sequences of randomization, that is, sphere then toric / toric then sphere. Independent paired T-test or Mann-Whitney test, as appropriate, was carried out to ensure there were no carry-over or period effects at the alpha level of 0.10.¹⁹ The differences in outcome measures between lens designs were examined using a linear mixed model, with fixed factors of sequence and contact lens design to obtain unbiased effect sizes. Estimated means, standard errors and medians and interquartile ranges were reported for each lens design. Estimated means, standard errors, and 95% confidence intervals of the differences between lens designs were also reported. In the presence of any carry-over effects, hypothesis tests were conducted on period one only. Significance was defined as P values of 0.05 or less.

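### The preference test pools both lens orders; a suitable exact test by sequence would use the randomised order at no cost in power (minor, one secondary outcome)

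*Protocol*

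**What the plan says.** Protocol section 5.2 makes preference a secondary outcome: "As a secondary outcome, subjects will be asked their preference of contact lenses in a two-alternative forced choice format". Its analysis is one sentence: "One-sample binomial tests will be used to test the hypothesis that the probability of preference" is the same for the two lenses. Lens order does not enter that test.

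The same section sets up the order: "We will randomize an equal number of subjects to each group", one group wearing the lenses in each order. It plans an independent t-test for carry-over and period effects and says that none are expected. On numbers it says: "A total of 30 subjects will be enrolled to allow for up to 20% dropout/screen-failure/missing data and have 24 subjects complete".

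The SAP (Statistical Plan) analyses the outcome measures with a linear mixed model that includes sequence. It tests carry-over on each subject's average over the two periods. It mentions neither preference nor the binomial test. Its significance rule is "Significance was defined as P values of 0.05 or less".

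**The concern.** A preference between two lenses can be given only after both have been worn. Under the visit timing in protocol section 8.1, the first lens is worn to about Day 10, the second is fitted at that same visit, and the study ends at about Day 20. The subject therefore weighs a current experience against one about ten days old. Some subjects may lean towards the more recent lens, whichever it is.

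The carry-over and period checks do not cover this. They need a measurement in each period, and preference is one binary answer per subject. Preference is thus a lens comparison for which neither document uses the randomised order.

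Two things are at stake:

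- **Power.** Recency adds choices that follow order and not lens, and so pulls the pooled proportion towards 50%.
- **The estimate.** If one sequence loses more subjects than the other, recency no longer cancels in the pooled proportion, and the reported toric preference moves up or down with the dropout pattern.

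**Working it through.** **Inputs from the documents.** 30 enrolled, 20% loss, 24 complete; equal allocation to the two orders; two-sided test at 0.05. The plan's own figure reproduces: 24 / (1 − 0.20) = 30. At 24 completers this is 12 per sequence. No power is stated for the preference test.

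**Assumptions.** The documents give neither a preference rate nor a recency size. The model is logit P(prefers toric) = θ + λ if toric is worn second, and θ − λ if it is worn first.
- θ = 1.1, so preference without recency is 1/(1 + e^−1.1) = 75%.
- λ = 0, 0.85 or 1.4. A subject with no lens preference then chooses the second lens with probability 50%, 1/(1 + e^−0.85) = 70%, or 1/(1 + e^−1.4) = 80%.

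**Step 1: the estimate.** At 70:30 recency:
- toric second: 1/(1 + e^−1.95) = 0.8754
- toric first: 1/(1 + e^−0.25) = 0.5622
- pooled, 10 toric-second and 14 toric-first: (10 × 0.8754 + 14 × 0.5622)/24 = 69.3%
- pooled, 14 and 10: (14 × 0.8754 + 10 × 0.5622)/24 = 74.5%
- mean of the two sequences, either split: (0.8754 + 0.5622)/2 = 71.9%

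The binomial test's power follows the same shift: 34.7% in the first split and 58.7% in the second.

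**Step 2: a test that uses order.** Recode each answer as choosing the second lens or not. With no lens effect, this probability is the same in both sequences, whatever the recency. A lens effect makes it differ. If d is the toric-second minus toric-first difference in that probability, d = 0.8754 − (1 − 0.5622) = 0.4376, and the mean toric preference is (1 + d)/2 = 71.9%. The test and the estimate therefore come from the same two-by-two table.

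**Step 3: exact power**, by enumerating every outcome in both sequences. At 24 completers the two-sided binomial test rejects at 18 or more, or 6 or fewer.

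| Completers | Recency | Binomial | Unconditional exact (pooled-z) | Fisher |
|---|---|---|---|---|
| 12 + 12 | none | 60.9% | 66.8% | 60.9% |
| 12 + 12 | 70:30 | 46.2% | 63.6% | 49.0% |
| 12 + 12 | 80:20 | 25.1% | 51.2% | 34.0% |
| 15 + 15 | none | 80.4% | 80.5% | 67.7% |
| 15 + 15 | 70:30 | 68.4% | 71.9% | 58.4% |

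Without recency, Fisher's test also falls behind the binomial at 14 + 14 (63.2% v 75.1%) and at 10 + 10 (42.2% v 61.8%). In every completer split enumerated, from 10 + 10 to 15 + 15, the unconditional test rejected whenever the binomial did.

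**Step 4: type I error.** At 12 + 12 with no lens effect and no recency, the binomial's actual level is 2.3% and the unconditional test's is 3.8%. Both stayed below 5% in all cases checked.

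**Step 5: what the gain consists of.** The 5.9-point gain at 12 + 12 without recency (66.8 − 60.9) is not order adjustment. It arises because the binomial test uses only 2.3% of its nominal 5% at that size. At 15 + 15 both tests have an actual level of about 4.3%, and the gain is 0.1 points without recency and 3.5 points at 70:30.

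**The case against.** The strongest reply is that the planned test does its job. Equal randomisation makes symmetric recency largely cancel under the null, no false-positive risk appears, and the protocol does not expect period effects. Preference is one secondary outcome with no power target. With mild recency the loss is small: at a recency odds ratio of 1.5 and a preference of exactly 75%, binomial power at 12 + 12 falls only from 60.7% to 57.4%. The loss also depends on the model. If the preference averaged over both orders is held at 75%, binomial power stays near 61% (61.1% at an odds ratio of 3). All of this stands, and it makes the point one of efficiency and estimation, not validity.

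A second reply is that adjusting for order costs power. That is true of Fisher's test at 10 + 10, 14 + 14 and 15 + 15, and the last of these is full retention of the 30 enrolled. It is not true of the unconditional test.

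Two stronger readings are tempting. A reader might infer that the binomial test is biased towards a false toric preference; the calculations show no inflated error. A reader might also infer that the investigators considered an order-adjusted test and set it aside to save power. Neither document says so: the protocol names the binomial test without a reason, and the SAP is silent on preference.

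**Conclusion.** The point holds as a minor improvement. The planned binomial test is valid but leaves the randomised order unused, and its pooled proportion depends on which sequence loses subjects if recency exists. Under 75% preference and 70:30 recency, a 10/14 imbalance moves the expected estimate to 2.6 points below (69.3%) or above (74.5%) the 71.9% sequence average. The power gain from an unconditional exact test at 70:30 is 17.4 points at 12 + 12 (63.6 − 46.2), part of which is the binomial's discreteness, and 3.5 points at 15 + 15. These sizes rest on assumed preference and recency. If there is no recency, the estimate is unaffected and the change costs no power at any split examined. It does not follow that any stratified exact test would do, so the test has to be named.

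**What to change.** Add to the preference analysis: compare the proportion choosing the second lens between the two sequences with a two-sided unconditional exact (Barnard-type, pooled-z) test at 0.05. Report toric preference as the mean of the two sequence-specific proportions, with a confidence interval obtained by applying (1 + d)/2 to the limits for the difference d. Show the counts by sequence. Do not specify Fisher's exact test.

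The cost is a sentence or two of analysis wording. The only data needed are each subject's recorded choice and randomised order, with no extra subjects or visits. The SAP is dated 20 Dec 2021 and written in the past tense. If preference has already been analysed, keep the planned binomial result, give the sequence-based result beside it, and label the latter as added.
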